3.3 Secondary Endpoints

Proportion of patients achieving complete or partial remission where the responses are defined as below:

- a) Complete Response at 12 months
 - < 300 mg proteinuria/24 hours
 - No greater than a 15% reduction in GFR as determined by creatinine clearance
- b) Partial Response at 12 months
 - > 50% reduction in 24 hour proteinuria
 - No greater than a 30% reduction in baseline GFR as determined by creatinine clearance
- c) No Response at 12 months
 - \leq 50% reduction, unchanged or increasing proteinuria over baseline levels

- A greater than a 30% reduction in baseline GFR as determined by creatinine clearance
- d) Improvement in hematuria (Categorical: <3 rbc/hpf; 3-10 rbc/hpf; 10 to 50; 50 to 100; >100 rbc/hpf)
- e) Improvement in complement 3 level (increase of 25% from baseline)

4 Subject Selection Enrollment and Withdrawal

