4.3 Subject Recruitment, Enrollment and Screening

- Patients will be recruited from the principal investigator or co-investigator clinical practices
- Referring nephrologist within the Division of Nephrology and Hypertension at Mayo Rochester
- Review of renal biopsies and lab values conducted as part of clinical care
- Patients will receive \$1000 remuneration total for study participation (\$40 per completed study visit). Five hundred dollars will be given after completion of the 16th and final infusion, which is study visit Day 162. Five hundred dollar will be given after completion of the final visit on Day 365. If the patients withdraw from the study for any reason, they will receive prorated remuneration at \$40 per completed study visit.

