4.4 Early Withdrawal of Subjects

4.4.1 When and How to Withdraw Subjects

- Subjects decision to withdraw from the study (withdrawal of consent)
- Failure of subject to adhere to protocol requirements (missing more than two infusions within the first 8 weeks or more than three infusions in the following 4 months). If a patient experiences an adverse event and the PI determines the next dose must be delayed, the dose may be delayed for up to 4 weeks and continue on the protocol schedule without being withdrawn.
- Disease progression (> 50% increase in proteinuria and > 30% reduction in GFR as measured by creatinine clearance) at day 77 visit
- Severe infection (defined as the development of pneumonia, severe urinary tract infection/pyelonephritis, sepsis, meningitis)
- If Hgb < 8.0 g/dL or platelet < 50,000, or WBC < 3.0 or absolute neutrophil count (ANC) < 500, the infusion will be held and restarted once blood counts have improved.

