4.4.2 Data Collection and Follow-up for Withdrawn Subjects

- Subjects that withdraw consent or are withdrawn from the study due to safety issues or not following through with the protocol will be followed clinically by the PI or co-investigators or will be sent back to the referring nephrologist

5 Study Drug

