5.5 Subject Compliance Monitoring

This drug is administered intravenously in the CRU and we can ensure compliance. If patient misses more than one infusion within the first 8 weeks or more than two infusions in the following 4 months the subject will be withdrawn from the study. We will continue to follow the subject as part of the research study with blood and urine studies and clinic visits to ensure safety.

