5.6 Prior and Concomitant Therapy

The patient should be off of all immunosuppressive therapies (cyclophosphamide, MMF, cyclosporine, tacrolimus, azathioprine, ACTH) within three months of enrollment in the study. If patient has received rituximab prior to the study there should be evidence of B-cell reconstitution prior to enrollment (CD 20 count >5). The subject should be off of prednisone or glucocorticoid equivalent in the last 6 weeks prior to enrollment, unless they are being treated with low dose oral prednisone or glucocorticoid for a condition unrelated to PGNMID or C3GN (e.g., asthma, gout) at a daily dose of 10mg or less.

Patients can receive ACE-I or ARB while enrolled in the study but dose adjustment is not allowed unless down titration for safety reasons.

Rescue treatment is not permitted while receiving daratumumab. If patient is failing treatment with evidence of disease progression (> 50% increase in proteinuria and > 30% reduction in GFR based on creatinine clearance) on visit day 77, the subject will be withdrawn from the study and can then receive other immunosuppressive therapy per discretion of the treating physician.

Management of Hepatitis B Virus Reactivation

Primary antiviral prophylaxis is permitted as per local standard of care. Per protocol, HBV DNA testing by PCR is mandatory for subjects at risk for HBV reactivation see Section 6.

For subjects who are diagnosed with HBV reactivation while on treatment, study treatment should be interrupted until the infection is adequately controlled. If the benefits outweigh the risks, study treatment may be resumed with concomitant antiviral prophylaxis as per local standard of care. Consult a liver disease specialist as clinically indicated.

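### The bar on rescue therapy stops with daratumumab dosing, but remission is scored about 203 days later with no rule for patients who have started another agent in between

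*Combined protocol and SAP*

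**What the plan says.** **Rescue.** Section 5.6 says that "Rescue treatment is not permitted while receiving daratumumab". The only stated route to other immunosuppression is for a patient with disease progression at the Day 77 visit, who is withdrawn and "can then receive other immunosuppressive therapy per discretion of the treating physician".

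**End of dosing.** Section 4.3 ties a payment to "completion of the 16th and final infusion, which is study visit Day 162". Section 4.4.1 lets a dose be postponed after an adverse event: "the dose may be delayed for up to 4 weeks and continue on the protocol schedule".

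**Response.** Section 3.3 defines complete response and "Partial Response at 12 months" by 24-hour proteinuria and by change in GFR measured as creatinine clearance. Neither definition mentions other therapy.

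**Analysis.** Section 7.2 (Statistical Methods) summarises the proportion in complete or partial response and describes time to response by Kaplan-Meier. It also compares proteinuria and renal function at 6 and 12 months with baseline. The only analysis population is everyone who received at least one dose.

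**Other concomitant rules.** Section 5.6 bars ACE-inhibitor and ARB dose changes, apart from safety reductions, for as long as the patient is enrolled. Section 4.2 has MMF, cyclosporine, tacrolimus and azathioprine stopped when daratumumab starts.

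**Extension.** Under section 3.2, consenting patients in complete or partial remission are followed for a further 24 months. Section 7.2 counts time to relapse from the last daratumumab dose.

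**The concern.** The secondary objective in section 2 is remission that daratumumab induces. The response rule measures something slightly different: whether the patient meets the criteria on Day 365, whatever was given after dosing ended. The trial has one arm, so no comparison would show that an improvement came from another drug. The study is also open-label, so a scoring rule left unwritten would be settled by people who already know the result.

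The situation is plausible. Section 1.4 says most untreated patients progress to end-stage renal disease, and section 1.1 describes other regimens already in use at the centre. A patient not responding by Day 162 would have to wait more than six months for the assessment.

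For proteinuria the likely bias favours daratumumab, because rescue is given to lower it. For creatinine clearance the documents do not establish a direction. A misattributed remission would also enter the OLE relapse rate and time to relapse.

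**Working it through.** The plan states no power, alpha or target response rate (section 7.1), so there is no figure of its own to reproduce. The check is a reading of the rules, followed by simple arithmetic.

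**1. Length of the uncovered period.** Inputs: last infusion Day 162 (section 4.3); final assessment Day 365 (sections 4.3 and 6).
- On schedule: 365 - 162 = 203 days, and 203/365 = 56% of the study year.
- If one 4-week delay (section 4.4.1) shifts the whole schedule: 162 + 28 = Day 190, and 365 - 190 = 175 days.

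**2. Do the other rules close the gap?**
- ACE-inhibitor/ARB rule: runs for the whole of enrolment, so raising those doses is barred to Day 365. It does not concern immunosuppressive or clone-directed drugs.
- Stopping MMF, cyclosporine, tacrolimus or azathioprine at the start: says nothing about restarting after the last dose, or about new agents.
- Withdrawal reasons in section 4.4.1: starting other therapy is not among them.
- Day 77 route: covers progressors at that visit only. It gives no scoring rule even for them, although they remain in the all-treated population.

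**3. A patient taken through the rules.** Suppose proteinuria has fallen by 50% or less at the end of dosing. Another agent is started after Day 162. By Day 365 proteinuria is down by more than 50%, with no more than a 30% loss of GFR.
- Section 3.3: partial response.
- Section 7.2: in the population and in the numerator.
- Section 3.2: eligible for the OLE on consent, because the wording requires remission after daratumumab, not remission without other therapy.

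**4. Weight of one patient.** N = 12 (section 7.1), so 1/12 = 8.3 points. For illustration, section 7.2 expects 9 OLE entrants, who must be in remission. Taking 9 true responders, with exact (Clopper-Pearson) 95% intervals:
- 9/12 = 75.0% (42.8 to 94.5)
- 10/12 = 83.3% (51.6 to 97.9)

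The intervals overlap widely.

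**5. Expected inflation, under assumptions only.** Let p be the true response rate, r the share of non-responders rescued after the last dose, and s the share of those who then meet the criteria. Expected inflation = (1 - p) × r × s. None of p, r or s is given in the documents. I assume r from 0.10 to 0.50 and s from 0.3 to 0.5.
- p = 0.75 (9/12): 0.25 × 0.10 × 0.3 = 0.75 points, to 0.25 × 0.50 × 0.5 = 6.25 points.
- p from 0.3 to 0.5: lowest 0.5 × 0.10 × 0.3 = 1.5 points, highest 0.7 × 0.50 × 0.5 = 17.5 points.

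The spread comes entirely from the assumed inputs. It is not an estimate.

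**The case against.** **Silence is not permission.** The only sentence that allows other immunosuppression ties it to withdrawal. A reader might infer that the protocol permits rescue after Day 162. It does not say so, and that reading should not be adopted. What remains is that nothing forbids it, it is not a withdrawal reason, and no rule says how to score it.

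**Other rules limit concomitant treatment.** True, and they narrow the point. ACE-inhibitor/ARB increases are covered, and the listed immunosuppressants are stopped at the start. The gap concerns only new or restarted immunosuppressive or clone-directed therapy.

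**Scoring outcomes regardless of rescue is legitimate.** It can be. But the plan does not state that choice, and it answers a different question from the one in section 2.

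**The 6-month comparison.** A reader might infer that it is exposed in the same way. For on-schedule completers it is not: the Day 161 labs come before the last infusion. For patients withdrawn for missed infusions, section 5.5 says "We will continue to follow the subject as part of the research study with blood and urine studies", but it gives safety as the purpose. Section 4.4.2 says withdrawn patients "will be followed clinically by the PI or co-investigators or will be sent back to the referring nephrologist". The documents do not show that such values would enter the efficacy analysis.

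**Secondary, descriptive, twelve patients.** This stands in full. No test, power figure or go/no-go threshold depends on the response proportion.

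**Conclusion.** The point holds as a scoring gap. Followed exactly, the plan could credit daratumumab with a remission reached on another drug, because the bar on rescue ends with dosing and the 12-month definitions look only at proteinuria and creatinine clearance. The firm quantities are the uncovered period, about 203 days for an on-schedule completer, and 8.3 points per affected patient. The 12-month changes in proteinuria and renal function share the exposure.

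A reader might go further and infer that the reported response rate will be materially inflated. The documents do not support that. They give no rescue rate, and any percentage beyond the per-patient effect rests on assumed inputs. Nor is the primary safety objective affected. Priority: minor, a clarification worth making because it is cheap.

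**What to change.** **Section 3.3.** Add: a patient who starts non-study immunosuppressive or clone-directed therapy for PGNMID or C3GN before the 12-month assessment, including after withdrawal at Day 77, is scored No Response at 12 months and is not counted as a daratumumab remission for OLE entry. Except steroids given under section 5.4, and glucocorticoid of 10 mg/day or less for unrelated conditions.

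**Data capture.** Record such therapy with start dates through Day 365. The schedule in section 6, as legible, shows no concomitant-medication row.

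**Section 7.2.** Add three items:
- List these patients with therapy start date and response status before rescue.
- In the time-to-response summary, do not count a response first met after rescue as an event. Keep these patients in the denominator as non-responders; censoring them would be informative.
- Report the 12-month proteinuria and renal function changes as observed, with rescued patients flagged. Do not add an analysis that excludes post-rescue values: it would remove likely failures from the mean and tend to flatter daratumumab.

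**Cost.** A few sentences and a small amount of medication recording, with no new visits, tests or patients. The response rate may come out slightly lower and fewer patients may enter the OLE. A patient already in partial response who later adds an agent is scored No Response, which departs from the present definition, but the listing makes that case visible.

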5.7 Packaging

Commercially available supplies of daratumumab will be obtained for use in this study. Daratumumab is supplied in glass vials containing daratumumab at a concentration of 20 mg/mL. These will remain in the commercial packaging until prepared by the research pharmacy. After infusion preparation by the research pharmacy, the final infusion will be labeled as follows: "Caution: New Drug--Limited by Federal (or United States) law to investigational use."

5.8 Masking/Blinding of Study

This is an open-label study and all participants will be receiving the study drugs. There will be no blinding or masking.

5.9 Receiving, Storage, Dispensing and Return

5.9.1 Receipt of Drug Supplies

Janssen Scientific Affairs, LLC will ship the study medication directly to the Mayo Clinic Research Pharmacy. Mayo Clinic Research Pharmacy will ensure maintenance of complete and accurate records of the receipt, dispensation, and disposal of all the study drug in compliance with regulatory and institutional requirements.. Any discrepancies, damaged or unusable study drug in a given shipment (active drug or comparator) will be documented in the study files. The sponsor-investigator will be notified immediately of any discrepancies, damaged or unusable products that are received.

5.9.2 Storage

Research Pharmacy will store the study medication in a refrigerator specifically delegated for Research use only. The temperature is monitored electronically 24/7, 365 days/year. All study drug vials will be stored in a refrigerator ranging from 2°C to 8°C (36°F to 46°F) and will not be utilized after the expiry date printed on the label. The product must be protected from light so it will be kept in the boxes that it is shipped in until its use. The drug must not be frozen. Daratumumab does not contain preservatives; therefore any unused portion remaining in the vial must be discarded. The Research Pharmacy is a separate area within the Central Pharmacy. To enter the pharmacy, it requires identification badge scanning. Only pharmacy personnel have access to the pharmacy.

5.9.3 Dispensing of Study Drug

Regular study drug reconciliation will be performed to document drug assigned, drug dispensed, drug returns, and drug remaining. This reconciliation will be logged on the drug reconciliation form, and signed and dated by the study team.

5.9.4 Return or Destruction of Study Drug

At the completion of the study, there will be a final reconciliation of drug shipped, drug dispensed, drug returns, and drug remaining. This reconciliation will be logged on the drug reconciliation form, signed and dated. Any discrepancies noted will be documented and investigated, prior to return or destruction of unused study drug. Drug destroyed on site will be documented in the study files.

6 Study Procedures

See chart below

Test and Monitoring Schedule

Tests/ Assessments	Screening	D1, Inf 1	D8, Inf 2	D15, Inf 3	D21	D22, Inf 4	D29, Inf 5	D36, Inf 6	D43, Inf 7	D49	D50, Inf 8	D64, Inf 9	D77	D78, Inf 10	D92, Inf 11	D105	D106, Inf 12	D120, Inf 13	D133	D134, Inf 14	D148, Inf 15	D161	D162, Inf 16	D264	D365	OLE ⁸		
History/Exam ¹	X																							X	X			
Informed Consent	X																											
CBC with 5-part WBC differential	X				X					X		X				X			X		X	X	X					
Basic Metabolic Panel	X									X		X									X		X	X	X			
Albumin, serum	X											X									X		X	X	X			
Protein total, serum	X									X		X								X		X	X	X				
Protein electrophoresis, serum	X										X		X								X		X	X	X			
Immuno subtraction (immunofix), serum	X										X		X								X		X	X	X			
Hepatitis B tests ²	X																							X	X			
Hepatitis C tests	X																											
HIV test ³	X																											
Pregnancy test, serum ⁴	X																											X
Lipid panel	X																											X
Complement C-3 & C-4, serum	X																											X
Urinalysis w/microscopic	X											X		X							X		X	X	X			
Kappa & Lambda free light chain, serum	X											X		X							X		X	X	X			
Creatinine clearance	X											X		X							X		X	X	X			
Protein total, 24 hour urine	X											X		X							X		X	X	X			
Immunofixation, 24 hour urine	X											X		X							X		X	X	X			

Electrophoresis,24 hour urine	X									X			X							X		X	X	X	
Immunoglobulin quantitative IgA, IgG, IgM	X												X								X		X		
Indirect Antiglobulin Test (IAT) ⁵	X																								
Pregnancy Test, urine ⁶		X	X	X		X	X	X	X		X	X		X	X		X	X		X	X		X		
Pre-infusion medications ⁷ (methylprednisolone, acetaminophen and diphenhydramine		X	X	X		X	X	X	X		X	X		X	X		X	X		X				X	
Daratumumab Infusion		X	X	X		X	X	X	X		X	X		X	X		X	X		X	X		X		
Adverse Events			X			X		X			X			X			X			X		X	X	X	

1 Exam will include vitals (i.e., height, weight, temperature, blood pressure and pulse)

2 Subjects If hepatitis B results are positive HBV testing by PCR will be performed. Subjects who are positive for Anti-HBc or Anti-HBs will undergo testing for hepatitis B DNA by PCR. Subjects with serologic findings suggestive of HBV vaccination (Anti-HBs positivity as the only serologic marker) and a known history of prior HBV vaccination do not need to be tested for HBV DNA by PCR. During and following study treatment, subjects who have history of HBV infection will be closely monitored for clinical and laboratory signs of reactivation of HBV as specified in the Test and Monitoring Schedule Table above. Local law requires positive test results be reported to local health authorities.

3 If HIV or Hepatitis C test results are positive a reflex test will be conducted to confirm. Local law requires positive test results be reported to local health authorities.

4 Serum pregnancy test for women with childbearing potential.

5 Daratumumab treatment affects pre-transfusion blood testing. Therefore, in the event that a patient may need a blood transfusion Indirect Antiglobulin Testing will be performed at screening, prior to the first daratumumab infusion, and the results given to patients to carry for the duration of the study.

6 Urine pregnancy test prior to infusion for women with childbearing potential.

7 Pre-infusion medication methylprednisolone given prior to first infusion and only as needed for subsequent infusions for infusion reactions. Pre-infusion medications acetaminophen and diphenhydramine given prior to all infusions.

8 In the OLE patients will be followed clinically every 3 to 6 months, as determined by the treating nephrologist in consultation with the PI. If there is evidence of relapse defined as a 30% increase in their proteinuria from the lowest proteinuria level that the patient had achieved, patients will be treated with 12 additional doses daratumumab at 16 mg/kg.

7 Statistical Plan

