4.2 Exclusion Criteria

- Pregnancy
- Seropositive for human immunodeficiency virus (HIV)
- Seropositive for hepatitis B (defined as a positive test for hepatitis B surface antigen [HBsAg] Subjects with resolved infection (ie, subjects who are HBsAg negative but positive for antibodies to hepatitis B core antigen [anti-HBc] and/or antibodies to hepatitis B surface antigen [anti-HBs]) must be screened using real-time polymerase chain reaction (PCR) measurement of hepatitis B virus (HBV) DNA levels. Those who are PCR positive will be excluded. EXCEPTION: Subjects with serologic findings suggestive of HBV vaccination (anti-HBs positivity as the only serologic marker) AND a known history of prior HBV vaccination, do not need to be tested for HBV DNA by PCR)
- Seropositive for hepatitis C (except in the setting of a sustained virologic response [SVR], defined as aviremia at least 12 weeks after completion of antiviral therapy).
- Multiple myeloma
- Anemia with Hgb $<$ 8.5 g/dL
- Thrombocytopenia with platelet count $<$ 100,000
- Leukopenia with WBC $<$ 3.5
- Any other disease, metabolic dysfunction, physical examination finding, or clinical laboratory finding giving reasonable suspicion of a disease or condition that contraindicates the use of an investigational drug or that may affect the interpretation of the results or render the patient at high risk from treatment complication
- Unable to provide consent
- Patients receiving therapy with oral prednisone or glucocorticoid equivalent in the last 6 weeks. Patients treated with low dose oral prednisone or glucocorticoid are allowed to be included if they are taking the medication for conditions unrelated to PGNMID or C3GN (e.g., asthma, gout) at a daily dose of 10mg or less.
- Patients who had received immunosuppressive therapy with cyclophosphamide, in the last 3 months

- Patients treated with MMF, cyclosporine, tacrolimus or azathioprine are allowed to be included if proteinuria has not improved or is worsening despite these medications and/or kidney function is worsening despite treatment with any of these medications. Once treatment with daratumumab is started, these medications will be discontinued.
- Patients who received rituximab previously with CD20 count of zero at the time of enrollment

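### Hepatitis B reactivation monitoring is promised during treatment as set out in the schedule, but the schedule's hepatitis B row shows no test across at least the first 15 of 16 infusions

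*Combined protocol and SAP*

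**What the plan says.** Four places in the combined protocol and SAP bear on this.

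- **Section 4.2 (Exclusion Criteria).** Subjects with resolved hepatitis B (surface antigen negative, core and/or surface antibody positive) are screened by HBV DNA PCR. "Those who are PCR positive will be excluded"; the PCR-negative ones may enrol.
- **Section 5.6, on HBV reactivation.** "HBV DNA testing by PCR is mandatory for subjects at risk for HBV reactivation see Section 6". No timing is given there. For reactivation diagnosed on treatment, "study treatment should be interrupted until the infection is adequately controlled". Antiviral prophylaxis is permitted under local practice.
- **Section 6, footnote 2 to the Test and Monitoring Schedule.** The commitment covers the time on drug and the time after it: "subjects who have history of HBV infection will be closely monitored for clinical and laboratory signs of reactivation of HBV as specified". The place named for the timing is the table itself: "as specified in the Test and Monitoring Schedule Table above".
- **Section 6, the schedule itself.** The row labelled "Hepatitis B tests" has three marks: screening, and two adjacent marks at the right-hand end, under D264 and D365 as the table was read. Scheduled blood chemistry is a basic metabolic panel, albumin and total protein. There is no liver-enzyme row.

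**The concern.** The text makes a specific safety commitment (laboratory monitoring while the patient is on drug) and hands the timing to a table that appears to contain none. Section 5.6 sends the reader to Section 6. Footnote 2 in Section 6 sends the reader to the table. The table's hepatitis B row is empty over the infusion period.

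At stake is whether a site that follows the schedule to the letter would have any planned laboratory result that could bring the Section 5.6 interruption rule into play during main-study treatment. Safety is the primary objective (Section 2), and the protocol itself singles out this risk with its own management paragraph. A gap between promise and schedule therefore matters even in a 12-patient study.

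**Working it through.** No sample-size or power figure is involved. The check reads the schedule against the text and tests how far the reading depends on column alignment.

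**1. Can at-risk patients be in the trial?** Yes. Section 4.2 excludes on PCR positivity, not on antibody evidence of past infection.

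**2. Is the column header reliable?** The daratumumab row has 16 marks, and they fall exactly on the 16 columns labelled as infusions. The last is D162, which agrees with Section 4.3. Numbering the columns from Screening = 1, D148 (infusion 15) is column 21, D161 is 22, D162 (infusion 16) is 23, D264 is 24, D365 is 25 and OLE is 26.

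**3. Where are the hepatitis B marks?** In columns 1, 24 and 25. Columns 2 to 23 (D1 to D162) hold none.

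**4. How much do other rows drift?**
- Section 8 gives the CBC days as D21, 49, 77, 105, 133, 161, 264 and 365. The last two should be columns 24 and 25 but were read at 22 and 23, so that row drifts left by up to two columns.
- The pre-infusion medication row has its last mark under D264 instead of D162, a drift right of one. It also shows 15 marks where footnote 7 implies 16.
- The serum pregnancy, lipid and C3/C4 rows each have a mark two columns beyond OLE.

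Drift of one or two columns in either direction is therefore the range to test.

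**5. What does drift do to the hepatitis B row?**

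| True position relative to the reading | Late marks | Infusions given before the day of the first post-screening test |
|---|---|---|
| Two columns earlier | D161, D162 | 15 |
| One column earlier | D162, D264 | 15 (the 16th is on the same day) |
| As read | D264, D365 | 16 |
| One column later | D365, OLE | 16 |
| Two columns later | OLE and beyond | 16 |

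Even in the most favourable case the first post-screening test comes 161 − 1 = 160 days after the first infusion. Moving the first late mark to D105 (column 16) would need a shift of 24 − 16 = 8 columns, far more than any drift identified above.

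**6. Does another scheduled test fill the gap?** No row lists liver enzymes. Adverse-event enquiry is scheduled through treatment (Section 6 table; Section 8), but it is general and is not a laboratory measure.

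**7. What about the OLE?** As read, the hepatitis B row has no mark in the OLE column, and footnote 8 names no HBV test for a 12-dose retreatment course.

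**8. How many patients?** The documents do not say. Purely as an assumption, if 5% to 15% of patients had evidence of past infection, the expected number is 12 × 0.05 = 0.6 to 12 × 0.15 = 1.8. The chance that none of the 12 is at risk is 0.95^12 = 54% to 0.85^12 = 14%. The contradiction does not depend on this range.

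**The case against.** The strongest objection is that the table is damaged. Marks have moved in both directions, and the pre-infusion row is one short, so a mark could also be missing from the hepatitis B row. The small number of marks does not settle the matter: quantitative immunoglobulins has four marks in all, some of them on treatment, so a sparse row is not necessarily an off-treatment row. This stands as a reason to check the original. It does not remove the finding, because drift of the size seen elsewhere cannot place a test before infusion 15.

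The PCR sentence in Section 5.6, taken alone, could also be met by PCR at screening. That is fair. The conflict rests mainly on footnote 2, which covers the treatment period in terms and names laboratory signs.

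Three stronger readings are tempting, and the documents do not support them.

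- **An exact gap.** A reader might quote 264 − 1 = 263 days without a test, ending 264 − 162 = 102 days after the last infusion. Those figures hold only if the columns are exactly as read.
- **Reactivation would go unnoticed, or could not be reported.** Section 8.2 requires questioning about adverse events at each contact and recording of all of them. Footnote 2 covers clinical as well as laboratory signs. Nothing forbids an unscheduled test, and the interruption rule acts on a diagnosis however it is reached.
- **A late result comes when no treatment is left to interrupt.** Section 7.2 expects 9 patients in the OLE, and the Study Summary allows up to three courses over 24 months, so a late result could precede retreatment.

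Finally, HBV is not named in any endpoint or stopping rule, prophylaxis is permitted, and possibly no enrolled patient is affected. All true. These points limit the likely impact but do not make the text and the table agree.

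**Conclusion.** The inconsistency is real. The text promises laboratory monitoring for HBV reactivation during treatment and says the schedule specifies it. The schedule, as it can be read, has no HBV laboratory test from the first infusion through at least the fifteenth, and no liver-enzyme test at any time. The interruption rule therefore has no scheduled laboratory trigger for almost all, or all, of main-study treatment. It could still be triggered by symptoms, adverse-event enquiry or an unscheduled test.

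The conclusion assumes that column drift in this row is no larger than the one or two columns seen elsewhere, and that no on-treatment hepatitis B mark was lost in reading the table. Both can be settled by looking at the original. The number of patients affected is unknown and may be zero. The point is worth acting on because it concerns a stated safety commitment and is cheap to repair.

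**What to change.** First confirm the hepatitis B row against the original table. Then reconcile Section 5.6, footnote 2 and that row, so that the table specifies the on-treatment HBV laboratory monitoring the text already promises. The same reconciliation should cover any OLE retreatment course. Because footnote 2 speaks of a history of infection and Section 5.6 of being at risk, the amended text should also define one group to whom the monitoring applies. The sponsor decides which tests and when; this review proposes neither.

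The cost is an amendment to one table row, its footnote and the cross-reference in Section 5.6. Section 8 already schedules a CBC at D21, 49, 77, 105, 133 and 161, so sampling can use existing draws without extra main-study visits. The downside is a small assay cost in the few, possibly zero, at-risk patients.
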